Appendix 1. List of Variables

VARIABLE	MEASURE	TIME OF ASSESSMENT						
		SCREENING	BASELINE	SESSION-WISE	3 MONTHS	6 MONTHS	12 MONTHS	HOME VISIT
PRIMARY OUTCOME								
Depressive symptoms	Edinburgh Postnatal Depression Scale (EPDS)							
SECONDARY OUTCOMES								
Depressive symptoms	Edinburgh Postnatal Depression Scale (EPDS)							
Anxiety Symptoms	General Anxiety Disorder-7 (GAD-7)							
Child Mental Development	Bayley-IV							
Psychosocial Stimulation	Home Observation Measurement Evaluation (HOME)							
EXPLORATORY OUTCOMES								
Response & Remission	Patient Health Questionnaire (PHQ-9)							
Suicide Risk*	Columbia Suicide Severity Risk Screener (C-SSRS)							
Patient-Reported Activation	Premium Abbreviated Activation Scale (PAAS)							
Quality of Life Assessment	EQ5D-5-level (EQ5D-5L)							
Perceived Support	Multidimensional Scale of Perceived Social Support (MSPSS)							
Trauma Symptoms	Post-Traumatic stress disorder checklist (PCL-6)							
Patient Satisfaction	Client Satisfaction Questionnaire (CSQ-8)							
Therapeutic Alliance	Working Alliance Inventory – Short Revise (WAI-SR)							
Disability Assessment	World Health Organization Disability Assessment Schedule 2.0 (WHODAS 2.0)							
Dosage	Treatment Log: number of sessions attended							
Homework Adherence	Treatment Log: degree of activation							
COVID-19 exposure	COVID-19 Exposure (Y/N)							
Health Services Utilization	Health Service Utilization Questionnaire (HSU-Q)							
Health Benefits Access and Use	Health Benefits Questionnaire							
Medications	Currently taking medication (Y/N): • If yes, list: _____							

Medication	Change in medication since last time the [medication] questionnaire was completed (Y/N)							
Screening: Alcohol use	Alcohol use disorder identification test (AUDIT)							
Screening: Treatment Preference	Treatment Preference (IP/TM)							
Maternal Characteristics: Age	Self-reported age (years)							
Maternal Characteristics: Immigrant status	Born in the country of current residence (Y/N)							
Maternal Characteristics: Immigrant status	Duration (years) lived in Canada/USA							
Maternal Characteristics: Ethnicity (MC)	Self-reported ethnicity							
Maternal Characteristics: Residence	Duration (years) of residence in current home							
Maternal Characteristics: Education Level (MC)	Highest level of education completed							
Maternal Characteristics: Marital status (MC)	Marital status							
Maternal Characteristics: Occupational status (MC)	Current employment/work status							
Maternal Characteristics: Income status (MC)	Household Income (before taxes)							
Maternal Characteristics: Income status (MC)	Ability to manage on current family income							
Maternal Characteristics: Mental health history	History of depression or anxiety (Y/N)							
Maternal Characteristics: Mental health history	History of depression related to birth of baby							
Maternal Characteristics: Mental health history	Age of first depression/anxiety							
Maternal Characteristics: Mental health history	History of seeing therapist							
Maternal Characteristics: Mental health history	Months of therapy since last session in the last year							
Maternal Characteristics: Psychosis symptoms	Psychosis screener							
Maternal Characteristics: Mania symptoms	Mania symptoms							

Maternal Characteristics: Drug use	Drug use screener							
Maternal Characteristics: Medical history (MC)	Medical conditions 
 • High BP, PCOS, Diabetes, Kidney disease, Autoimmune disease, Thyroid disease, Obesity, HIV/Aids, None, Not wish to answer 							
Maternal Characteristics: Medical history (MC)	Medication. If yes: 
 • Over the counter. List: _____ • Prescription. List: _____ • Herbal. List: _____ 							
Maternal Characteristics: Medical history	Alcohol use (Y/N/Y but not while pregnant)							
Maternal Characteristics: Medical history	Alcohol use frequency							
Maternal Characteristics: Medical history	Cannabis use (Y/N/Y but not while pregnant)							
Maternal Characteristics: Medical history	Cannabis use frequency							
Maternal Characteristics: Sexual orientation and gender identity (MC)	Gender identity							
Maternal Characteristics: Sexual orientation and gender identity (MC)	Sexual orientation							
Maternal Characteristics: Sexual orientation and gender identity (MC)	Gender identity of partner							
Perinatal history: Pregnancies	Pregnant (yes/no)							
Perinatal history: Pregnancies	Weeks pregnant or post-partum							
Perinatal history: Pregnancies	Intentional pregnancy (yes/intentions kept changing/no)							
Perinatal history: Pregnancies	History of pregnancies							
Perinatal history: Miscarriages	History of miscarriages (< 20 weeks)							
Perinatal history: Still birth	History of still births (>= 20 weeks)							
Perinatal history: Infant death	Infant death (if postpartum)							
Perinatal history: Preterm labor	History of preterm live births (< 37 weeks)							
Perinatal history: Abortion	History of abortions							

Perinatal history: Medical history	History of ectopic pregnancy							
Perinatal history: Medical history (MC)	Pregnancy conditions 
 Pre-eclampsia, High blood pressure, Gestational diabetes, Preterm labor 							
Perinatal history: Medical history (MC)	Medications during pregnancy 
 Insulin, Glyburide, Metformin, Betamethasone, Progesterone injections or suppositories to prevent preterm birth 							
Perinatal history: Pregnancies	Most recent delivery (singleton, twins, triplets, quadruplets)							
Perinatal history: Child	Child date of birth							
Perinatal history: Child	Child sex							
Perinatal history: Child	Child due date							
Perinatal history: Child	Child birth weight							
Perinatal history: Child	Child birth length							
Perinatal history: Child (MC)	Pregnancy outcome of indexed child							
Perinatal history: Child	Fetal anomaly							
Perinatal history: Births	Previous births (count)							
Perinatal history: Number of children	Number of children							
Perinatal history: Labor (MC)	How labor began (on own, induced, Caesarean)							
Perinatal history: Labor (MC)	Planned method of delivery (Vaginal, Caesarean section)							
Perinatal history: Labor (MC)	Medication for pain during recent labor and delivery							
Perinatal history: Labor	Pitocin (Oxytocin) at any point before your baby was born							
Perinatal history: Labor	Bleeding after delivery							
Perinatal history: Labor	Blood transfusion (Y/N)							
Perinatal history: Labor	Baby admitted to NICU after delivery							
Perinatal history: Breastfeeding	Plan for feeding infant							
Perinatal history: Breastfeeding	Pain, if any, breast feeding during the following time periods							

Notes: MC=Multiple Choice.

TREATMENT PROVIDER VARIABLES			
VARIABLE	MEASURE	TIME OF ASSESSMENT	
		ENROLLMENT	SUPERVISION SESSION-WISE
Provider characteristics: Age	Self-reported age (years)		
Provider characteristics: Sexual orientation and gender identity (MC)	Gender		
Provider characteristics: Sexual orientation and gender identity (MC)	Gender Identity		
Provider characteristics: Sexual orientation and gender identity (MC)	Sexual orientation		
Provider characteristics: Ethnicity (MC)	Ethnicity		
Provider characteristics:	Designation (NSP/SP)		
Provider experience	Experience implementing evidence-based psychological treatments prior to SUMMIT (Y/N)		
Provider experience	Experience seeing patients using telemedicine prior to SUMMIT (Y/N)		
Weekly Supervision	Provider Attendance		
Measurement-Based Supervision	Q-SUMMIT (Adapted from Quality of Healthy Activity Program: Q-HAP)		
Therapy Quality	Q-SUMMIT (Adapted from Quality of Healthy Activity Program: Q-HAP)		

Notes: MC=Multiple Choice.

Other forms collected, when applicable:

- *Columbia Suicide Severity Rating Scale – Cox and Holden completed at any time point if a participant:
 - Has a positive verbal response to self-harm
 - Scores >0 on question 10 of the EPDS
 - Scores >0 on question 9 of the PHQ-9
- Infant Harm By A Child
- Infant Harm By Other Adult
- Infant Harm By Study Participant
- S/AEs

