Intervention Costs	A survey of costs associated with the intervention	Self-reported and health records, related to the economic evaluation portion of the study
Treatment: Measured at every	session during treatment, unless otherwise indicated	
Dosage	Treatment Log 	Frequency of Sessions Attended
Therapy Quality****	Quality of Healthy Activity Program (Q-HAP)52	Mean continuous score of treatment-specific BA skills (0-4) and general counseling skills (0-4)
Session Depressive / Anxiety	Session-by-session EPDS  and GAD-7  scores	Mean continuous score of a 10-item scale (0-30) on EPDS and of a 7-item scale (0-21) on GAD-7
Homework Adherence	Treatment Log 	Mean continuous score of a 1-item question (0-2)
Adverse or Serious AEs	Anytime an Adverse Event (AE) or Serious AE occurs	Any event that represents a series threat to the safety of the mother or her child (see Appendix D)
Health Service Utilization	Health Service Utilization Form 	Total score of a 16-item scale (0-32)
List of Medications	List of Medications	Self-reported list of medications
COVID-19 Exposure	1-item question on COVID-19 exposure	Self-reported
Child: Measured at 6 to 24-more	nths post-child birth unless otherwise indicated	
Birth weight & Length	Retrieved from hospital chart or self-report†	Assessed at birth

Breastfeeding	Whether breastfeeding and if stopped age stopped.54	Total Number of Months (0-12)
Psychosocial Stimulation	Home Observation Measurement Evaluation 	Total score of a 45-item checklist
Mental Development	Bayley Mental Development Scales IV 	Mean continuous score of cognitive, receptive and expressive language development

\* Assessment period will be extended to account for post-treatment outcomes when there are perinatal-related interruptions to treatment (e.g., giving birth, obstetrical complications, COVID-19); \*\*Only at baseline; \*\*\*Measured at 3-months post-randomization only; \*\*\*\*Randomly selected for supervision, rated by self, peers, expert supervisor; †Self-report will be used when hospital charts are outside of the recruiting site; Measured at baseline for participants consented after addition of measure to baseline questionnaire, measured at 12-months post-randomization for those who completed baseline before addition of measure; Deasured once at 3-, 6- or 12-months post-randomization.

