#### 2.10. Economic Evaluation

We will evaluate the cost-effectiveness of non-specialist providers and telemedicine, compared to specialist providers and in-person sessions. We will undertake a cost-utility analysis conducted at the 12-month post-randomization follow-up point. The primary outcome will be quality-adjusted life years (QALYs) calculated using the EuroQol 5 Dimension 5 Level (EQ-5D-5L) measure of health-related quality of life, collected at 3, 6 and 12-months.

- **2.10.1. Economic-related data.** The primary outcome related to the economic evaluation is quality adjusted life years (QALYs) calculated using the EuroQol 5 Dimension 5 Level (EQ-5D-5L) measure of health-related quality of life. An advantage of the EQ-5D-5L is that an overall utility score of health-related quality of life can be obtained, which facilitates comparisons with other interventions and health states in other illnesses.
- **2.10.2. Service use.** The use of all health services, other than the intervention (BA), are being recorded using an adapted version of the health services utilization questionnaire (HSUQ). Data on the use of BA (number and duration of therapy contacts and with whom) will be collected from existing clinical records. This measure (*see Health Service Utilization Questionnaire, Appendix C Study Measures*, pg. 35) was adapted with reference to other measures used in perinatal depression populations and for use in Canadian and US contexts with input from service users and clinicians. It will be completed at baseline (covering the last 3 months) and each follow-up interview (covering the period since the last interview). The HSUQ records use of health services, specifically: hospital inpatient stays,

outpatient appointments, emergency department visits and ambulance contacts, and community health contacts.

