#### 3.3. Participant Withdrawal

Participants can withdraw consent and end their participation in the study at any time. Non-completers and patients who do not respond to treatment will be referred to a trial psychiatrist or referred pathway (family physician, OBGYN, or external psychiatric services).

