In addition, we will run a linear regression model with mode, agent and a mode by agent interaction term to assess whether an interaction between mode and agent exists. In the unlikely event that randomization was not able to reduce bias by balancing out confounders, we will assess for confounding. This will be carried out by assessing each potential confounder individually in relation to the key predictor (mode or agent) and seeing if the potential confounder impacts the parameter estimate of the key predictor using the 10% change in estimate approach. The potential confounder would also need to be significantly related to the EPDS score outcome. Should any confounders exist, they'll will be included in all of the previously mentioned analyses. Rules on the number of variables allowed in a multivariable model will be followed. The rule on number of variables in a linear regression is to take the total number of observations divided by 10. Given our trial sample size, we will not have any concerns with overfitting our linear model for our covariates of interest (education level, marital status, ethnicity, baseline severity and chronicity, timing of treatment, compliance, perceived support and medication).

Our study statistician and two independent methodological consultants have reviewed and approved this plan of analysis.

**3.5.2. Secondary Analysis.** In our secondary analysis, we are interested in: i) assessing the trend in EPDS scores over time (baseline, 3, 6- and 12-months post-randomization) between

groups (telemedicine vs in-person, and specialist vs NSP). This will involve the use of linear mixed models adjusting for possible covariates including baseline depression symptoms, medication, treatment dosage, and child age when assessing child outcomes. Mothers will be taken as a random effect and the models will include a treatment- by- time interaction term; ii) the same set of analyses will be conducted for anxiety symptoms (GAD-7). All child outcomes, including child mental development and the provision of psychosocial stimulation by the mother, will be compared between two groups (antenatal vs. postnatal) at 6-24 months post-childbirth using a two-sample two-sided t-test. Sensitivity analyses will be carried out excluding those who dropped out after first session to see if the results are comparable to the entire study group. No interim analyses will be carried out.

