Depressive Symptoms ⁸	Edinburgh Postnatal Depression Scale (EPDS) ^{8,9}	Mean continuous score of a 10-item scale (0-30). Severity ranges: none or minimal depression (0-9), mild (10-11), moderate (12-19), severe (>19)
Anxiety Symptoms	Generalized Anxiety Disorder Scale (GAD-7) ^{10,11}	Mean continuous score of a 7-item scale (0-21). Cut-off value (10)
Response & Remission	Patient Health Questionnaire-9 (PHQ-9) ¹²	Response: PHQ<10 Remission is defined as PHQ<5
Perceived Support	Multidimensional Scale of Perceived Social Support (MSPSS) ¹³	Mean continuous score of a 12-item scale (1-84)
Disability Assessment	World Health Organization Disability Assessment Schedule (WHODAS) ¹⁴	Mean continuous score of a 12-item scale (0 – 48)
Quality of Life Assessment	EQ5D-5 Level (EQ5D-5L) ¹⁵	Mean continuous score of a 5-item scale (1-25)
Trauma Symptoms	Abbreviated PTSD Checklist (PCL-6) ¹⁶⁻¹⁸	Mean continuous score of a 6-item scale (1-30). Cut-off value [14 (threshold) and 8 (subthreshold)]
Patient-Reported Activation	Premium Abbreviated Activation Scale ^{19, 20}	Mean continuous score of a 5-item scale (0-20)
Patient Satisfaction***	Client Satisfaction Questionnaire-8 (CSQ-8) ²¹	Mean continuous score of an 8-item scale (1-32)
Therapeutic Alliance***	Working Alliance Inventory-Short Revise (WAI-SR) ²²	Mean continuous score of a 12-item scale (1-60)
Health Service Utilization	Health Service Utilization Questionnaire (HSU-Q) ²³	Total score of a 16-item scale (0-32)
Treatment Preference**	Delivery of treatment and treatment provider preference	Score of 0 or 1
COVID-19 Exposure ⁹	1-item question on COVID-19 exposure	Self-reported
Health Benefits Access and Use	2-item question on access and use of health benefits	Self-reported
Treatment: Measured at every session during treatment, unless otherwise indicated		
Dosage	Treatment Log ²⁴	Number of Sessions Attended
Therapy Quality****	Quality of Healthy Activity Program (Q-HAP) ²⁵	Mean continuous score of treatment-specific BA skills (0-4) and general counselling skills (0-4)
Session Depressive / Anxiety	Session-by-session EPDS ⁸ and GAD-7 ¹⁰ scores	Mean continuous score of a 10-item scale (0-30) on EPDS and of a 7-item scale (0-21) on GAD-7
Homework Adherence	Treatment Log ²⁴	Mean continuous score of a 1-item question (0-2)
Adverse or Serious AEs	Anytime an Adverse Event (AE) or Serious AE (SAE) occurs	Any event that represents a serious threat to the safety of the mother or her child (see Appendix D of protocol)

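### The 12-month arm comparisons in Protocol 3.5.2 may adjust for sessions attended and for medication at an unstated time point; adjustment should be limited to baseline variables

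*SAP*

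**What the plan says.** **Adjustment.** Protocol 3.5.2 sets out the secondary comparison of EPDS over baseline, 3, 6 and 12 months between the delivery modes and between the provider types, and repeats it for GAD-7. The method is "linear mixed models adjusting for possible covariates including baseline depression symptoms, medication, treatment dosage", with child age added for child outcomes. Protocol 3.5.1 and SAP 3.4.1 each list covariates of interest for the 3-month regression; both lists contain compliance and medication, and neither gives a time point for medication.

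**Recording.** SAP Appendix 1 has a baseline medication item under Medical history (over-the-counter, prescription and herbal). After baseline it has two items, "Currently taking medication (Y/N" and "Change in medication since last time the [medication] questionnaire was completed (Y/N". Both are ticked in the session-wise column and left blank at 3, 6 and 12 months. Protocol Table 6 describes the medication list as "Self-reported list of medications" and places it in the treatment block. SAP Table 2 does the same, under the banner "Treatment: Measured at every session during treatment, unless otherwise indicated". Dosage, the count of sessions attended, sits in the same block.

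**SAP rule.** SAP 3.4.1 limits adjustment in the primary regression to variables imbalanced at baseline. SAP 3.4.2.2 specifies a longitudinal model for antenatal against postnatal enrolment only, and names neither medication nor dosage.

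**The concern.** The arm contrast is protected by randomisation only while the model conditions on things fixed before randomisation. Sessions attended can depend on mode (travel, childcare, technology) and on provider. Medication started later can depend on how well the assigned strategy worked: Protocol 3.3 states that "Non-completers and patients who do not respond to treatment will be referred to a trial psychiatrist" or to another care pathway, and Protocol 4.4 provides referral information after a high post-treatment EPDS. Holding such a variable constant removes whatever part of the arm effect runs through it. It also mixes in the unmeasured reasons why women attend or are medicated. The estimate is then no longer the effect of assignment, although it would be read that way.

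Recording only at attended sessions adds a second problem if later medication is meant. The covariate would be missing for women who never start and, after the last session, for everyone. Those who leave treatment early lose it soonest, and they are among the women the protocol refers onward.

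**Working it through.** The plan gives no figure to reproduce, so the check sets the assessment schedule beside the model covariates and then asks what adjustment would do.

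**1. When each candidate covariate is measured (SAP Appendix 1)**

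| Variable | Baseline | Sessions | 3, 6, 12 months |
|---|---|---|---|
| Medication (Medical history) | yes | no | no |
| Currently taking medication | no | yes | no |
| Change in medication | no | yes | no |
| Dosage (sessions attended) | no | yes | no |

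Compliance is defined in Protocol 2.2.2 from sessions attended, so it too is post-randomisation. The Health Service Utilization form is completed at follow-up. According to Protocol 2.10.2, "The HSUQ records use of health services, specifically: hospital inpatient stays", followed by other visits and contacts; medicines are not in that list.

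**2. How much of the year the session record covers.** Inputs: 6 to 8 weekly sessions, and up to four months for compliance without a hiatus (both Protocol 2.2.2). Assumptions: prompt start, 12 months = 52.18 weeks, four months = 17.4 weeks.

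- 6 weeks: 6/52.18 = 11%; gap before month 12 = 52.18 − 6 = 46 weeks.
- 8 weeks: 8/52.18 = 15%; gap = 52.18 − 8 = 44 weeks.
- Four months: 17.4/52.18 = 33%; gap = 52.18 − 17.4 = 35 weeks.
- Never started: no post-baseline record at all.

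**3. What adjusting for later medication does.** In a linear model, adjusted arm difference = unadjusted difference − d × b. Here d is the arm difference in the share medicated and b is the model coefficient for medication. Suppose the worse arm uses more medication (d > 0).

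- If medicated women score higher because medication follows symptoms, b > 0 and adjustment shrinks that arm's deficit.
- If medication lowers scores enough, b < 0 and adjustment enlarges the deficit.

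The documents give neither d nor b. Purely as an assumed range, d of 0.05 to 0.15 and |b| of 1 to 3 EPDS points give shifts from 0.05 × 1 = 0.05 to 0.15 × 3 = 0.45 points, of either sign. A simulation with medication driven by earlier symptoms (13% medicated, d about 0.02) gave:

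- No drug effect: b = 2.11, d × b = 0.0203 × 2.11 = 0.043; the arm difference moved from 0.810 to 0.767.
- Drug effect of −2 points: b = 0.09, d × b = 0.0217 × 0.09 = 0.002; the difference was essentially unchanged (0.759 and 0.757).

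Sign and size therefore depend on inputs the plan does not supply.

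**4. What adjusting for dosage does.** Here too the direction is open. Few sessions can mean dropout. They can also mean quick improvement, because Protocol 2.2.2 lowers the required number after consistently low session EPDS scores.

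**5. How such variables could enter the 3-month regression.** Protocol 3.5.1 admits a covariate if it changes the arm estimate by 10% and is related to EPDS. A variable on the pathway from arm to outcome can pass both tests, so the rule does not screen out compliance or later medication. The baseline-imbalance rule in SAP 3.4.1 would, if applied literally, but its own covariate list still names compliance.

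**The case against.** The best defence is that the protocol speaks of possible covariates, that a baseline medication record exists, and that the SAP ties adjustment to baseline imbalance and leaves medication and dosage out of its longitudinal section. On that reading medication means baseline medication, and the medication half of the point disappears.

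Much of this stands: the documents do not establish that the models will use the later record. They do not exclude it either. In Protocol 3.5.2 the word baseline is attached to depression symptoms, while medication stands next to dosage, which can only be post-randomisation. The SAP does not replace the arm model: 3.4.2.2 specifies antenatal against postnatal, and the severity models in 3.4.2.3 name no adjustment set. The dosage half is untouched by the defence.

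A reader might go further in four ways that the documents do not support:

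- **That adjustment favours a finding of no difference.** The sign can go either way, as step 3 shows.
- **That a definite share of the non-inferiority margin is lost.** The margins belong to the 3-month t-tests, and the documents give no medication rates or effects. The 1.64 and 3.28 points in SAP 1.6.2.1 justify a margin from a psychotherapy effect; they are not drug effects.
- **That medicine costs are missing from the economic evaluation.** The form itself is in an appendix not among these documents, and Protocol 3.5.6 plans a retrospective record review to capture costs.
- **That medication items should be added at follow-up visits.** Recruitment ended in March 2023, the study period ended on 31 May 2024, and the protocol version is dated October 2024.

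**Conclusion.** The point holds as a limited one about secondary analyses. Protocol 3.5.2 allows the 12-month arm contrasts to be conditioned on sessions attended, which is post-randomisation on any reading, and on a medication variable whose time point is undefined. If that variable is the post-baseline record, it is unrecorded at every follow-up visit and for women who never start, and is unsuitable for adjusting an arm effect. If it is the baseline record, it is acceptable and only needs saying.

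The possible bias has no fixed direction, and its size cannot be estimated from the documents; the 0.05 to 0.45 points above rest wholly on assumed inputs. The coverage figures (11% to 15% of the year, or 33% if sessions run four months) assume prompt start and no hiatus. The primary 3-month t-test carries no covariates and is not affected. The regression that accompanies it could be, through compliance and medication.

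**What to change.** 1. In Protocol 3.5.2, remove treatment dosage and any post-randomisation medication from the models comparing modes and providers. State that medication means the baseline record in SAP Appendix 1 (Medical history: Medication).
2. In the covariates of interest in Protocol 3.5.1 and SAP 3.4.1, apply the same baseline-only restriction: remove compliance and specify baseline medication. Align the protocol's change-in-estimate rule with the SAP's rule of adjusting for variables imbalanced at baseline.
3. State in SAP 3.4.2.2 that the arm comparisons over time follow the same restriction, since that section currently gives no arm model.
4. Report post-randomisation medication and sessions attended descriptively by arm, noting that medication is not scheduled after the last session and is absent for women who never started.

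The cost is a few sentences across the two documents. No new data are needed, because baseline medication is already collected. What is given up is an arm estimate conditional on attendance or later medication, which would not be an effect of assignment.
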